4.7 Timeline of assessments

Assessments	B (Day 1)	MT (Day 1)	TMS (Day 2)	Post (Day 2)
Consent	X			
PANSS	X			X
CGI	X	X		
Edinburg handedness Questionnaire	X			
BACS	X			X

5. Subject Selection - Inclusion and exclusion criteria

Inclusion Criteria	Method of ascertaining
Inpatients with schizophrenia age group of 18-50	Self-report and clinical judgement
No other DSM diagnoses	Hospital chart
Right handed males and females	Edinburg handedness questionnaire
May have mild positive symptoms	Positive symptoms subscale(PANSS) ≤ 21
May have negative symptoms	Negative symptoms subscale (PANSS)
Ability to provide informed consent	Self-report
No restriction on concomitant medications given	Hospital chart
Exclusion criteria	
Intellectual disability	Hospital chart, clinical exam
Any organic brain illness	Hospital chart and clinical exam
Presence of dementia symptoms or traumatic brain injury	Hospital chart and clinical exam
Primary diagnosis of substance use	Hospital chart and clinical exam
Seizure disorder	Hospital chart and clinical exam
Actively symptomatic with PANSS positive symptom sub-scale >21 .	PANSS administration
Concurrently receiving ECT	

6. Subject recruitment and compensation

We will recruit inpatients from the inpatient unit at Duke Medical Center. Inpatients admitted on Williams' Ward in Duke South (4th floor red zone) will be approached for participation after discussion with their primary care team. Capacity to consent will be assessed by a member of the treatment team who is not an investigator on this study (such as the inpatient attending psychiatrist, nursing staff). Study team members (who are not members of the subject's clinical team) will approach potential subjects after the study is introduced to potential subjects first by the primary care team members. For both subjects, recruitment would proceed as follows: 1) study team member reviews charts of inpatients deemed eligible for the

Theta Burst Stimulation in Schizophrenia

study admitted at Duke Medical Center 2) Discuss with primary care team if the subject is appropriate 3) A member of patient's primary care team asks patient if they want to hear about study and 4) With patient agreement, study team member discusses study with them. Study team member discussing informed consent will fully disclose and explain the risks and benefits of the study procedures, and answer the patient's questions about the study and the material presented in the informed consent form. Alternatives to study participation will be discussed, and the voluntary nature of participation in the study will be emphasized. This consent discussion will be documented in a consent note placed in the patient's chart. Outpatients who wish to participate in the study will be screened over phone.

Patients would be compensated for their participation in the study. Subjects would be compensated for time spent in the study. Rate of compensation would be \$10/hour – amounting to a total of \$30. We do not plan to recruit subjects who are involuntarily committed on the unit. If they do appear as potential subjects while screening hospital charts, we will wait until they are converted to voluntary status before approaching them for recruitment into the study. Conversion of status from involuntary to voluntary occurs once subject's illness symptoms have improved and are closer towards remission.

7. **Consent Process** – see Section 14 of the e-IRB submission form
8. **Subject's Capacity to Give Legally Effective Consent** – All patients recruited for this study must have capacity to give legally effective consent. For consent, the study would be discussed with patient by study personnel and a member of their primary treating team will administer the University of California, San Diego Brief Assessment of Capacity to Consent (UBACC) to ascertain validity of the consent given for the study.

9. **Study Interventions** – This has been described in detail in section 4.3

10. Risk/benefit assessment

There are no known long-term health risks to the use of rTMS per se when operated within consensus safety guidelines(14). The Duke Medical Center Institutional Review Board recently classified two similar research applications of rTMS proposed by the PI as a “non-significant risk” (Protocols 20218 and 24349). In 2008, the FDA approved the use of high frequency rTMS in the treatment of depression. Also in 2008, an international consensus conference on safety guidelines for rTMS met, including representatives from our own labs (Drs. [name] and [name]). Their report (14) systematically reviewed the thousands of healthy subjects and patients who have undergone rTMS in order to allow for a better assessment of relative risks. The relative infrequency of adverse events using rTMS was noted. They concluded that in the case of Class 3 studies (studies involving indirect benefit and low risk in normal subjects and patients that are expected to yield important data on brain physiology or safety, but have no immediate relevance to clinical problems), normal volunteers should be permitted to participate in rTMS research when it is likely to produce data that are of outstanding scientific or clinical value. They also concluded that this research can be performed in a non-medical setting (i.e., psychology labs, robotics labs, research institutions, etc. as opposed to a hospital or appropriately equipped outpatient clinic). The Rossi et al. consensus report went on to suggest safety guidelines based on the now rather extensive international experience with rTMS. These guidelines include the rTMS intensity and timing parameters considered safe, training, and planning for and managing emergencies. We will follow these guidelines, and have incorporated them into our screening and session procedures.

Theta Burst Stimulation in Schizophrenia

Safety of theta burst stimulation

The Consensus Statement reached at the Sienna Meeting (14) updated previous guidelines includes information about asynchronous trains such as theta burst stimulation (TBS) paradigms including intermittent theta burst stimulation that would be the pattern of stimulation used in this study. A review of the safety of the procedure done by Oberman et al (2011) showed that the incidence of side effects was 0.5 % (Break down comprising headache or other craniofacial pain – 46 %, seizure 2%, muscle contractions 10 %, worsening tinnitus 6%, eye lacrimation 2%, lightheadedness 22%, nausea 2% and non-specific discomfort 10 %) (12). The reviewed population included 67 studies with a combined total subject number of 1040 people, and involving a total number of sessions exceeding 4,500. Of the 1001 subjects 776 were healthy control participants while 225 were clinical patients with both psychiatric and neurological diagnoses. 97 patients in this review received stimulation to the dorsolateral prefrontal cortex.

This review calculated the crude risk *per subject* for a seizure from theta burst stimulation to be 0.1 % while the crude risk per subject of mild adverse events (encompassing the remainder of the reported events) is 5% overall for both patients and healthy controls. As many studies involve multiple sessions of TBS, they calculated the crude risk of seizure *per session* of TBS as approximately 0.02%, and 1.1% for mild adverse events.

This meta-analysis also found that both the reported symptoms and general risk of adverse events during TBS is comparable to or less than other high frequency rTMS protocols (14). Seizure, the most severe reported adverse event, has only occurred once in over 4,500 sessions resulting in a crude risk of 0.02%, while the overall crude risk of any adverse event is estimated as 1.1%. This is comparable with other high frequency rTMS protocols where seizures have occurred in less than 0.1% of patients. The most common reported adverse event during TBS is also the most common in other rTMS protocols, transient headache and neck pain. This adverse event has been reported in up to 40% of patients undergoing high frequency rTMS and was experienced by less than 3% of the subjects receiving TBS. Participation in this study is completely voluntary, and there will be no pressure or time constraints regarding the decision to participate. There are no benefits to the participants except for the compensation, as well as the good will of helping the progress of scientific research. The information learned from this study may aid our understanding of the role of the theta burst stimulation in modulating cognition and brain function in patients with schizophrenia.

TMS Adverse Events Plan:

Seizure is a theoretical risk with rTMS. In the Rossi et al. report it was stated that “The occurrence of seizures has been extremely rare, with most of the few new cases receiving rTMS protocols exceeding previous guidelines, often in patients under treatment with drugs which potentially lowered the seizure threshold.” As Rossi et al. delineate, “rare” means that 16 cases (out of tens of thousands of rTMS sessions over the last two decades) of seizure related to rTMS have been reported. Eight occurred before safety parameters were established in 1997. Of the other eight reports, six occurred either when the safe rTMS parameters were exceeded or other safety guidelines ignored, and the actual occurrence of a seizure has been questioned in the other two (i.e., convulsive syncope or pseudoseizure may have occurred). In a workshop convened by the National Institute for Neurological Disorders and Stroke (NINDS) in 1996 (Duke investigators, [name], and [name] were participants), researchers in the field agreed upon a set of rTMS consensus safety guidelines, including recommended stimulation parameters and contra-indications (15), and these consensus guidelines have been recently updated (Rossi et al., 2009). Widespread adherence to the 1996 guidelines has resulted in the virtual elimination of inadvertent seizures in rTMS studies (Rossi et al., 2009). The levels of stimulation used in this protocol are well within safety guidelines (Rossi et al., 2009; Wassermann et al. 1998).

Theta Burst Stimulation in Schizophrenia

We will screen subjects for known risk factors for seizure with rTMS (medical screening and medical history). Personnel who administer rTMS are trained to recognize a potential seizure event and to act as “first responders” to administer appropriate initial care. All study personnel have undergone Basic Life Saving training, and seizure-specific training. The major physical signs the study personnel will look out for in detecting a potential seizure include chewing movements, convulsions/tremor/shaking, difficulty talking, a blank stare, eyes rolling up, and profuse sweating. If any of these signs are observed, study personnel will stop the research procedure and inquire whether the subject feels okay. If the subject is unresponsive (and therefore likely experiencing a seizure), first-aid will be supplied. The first-aid response consists of making sure the subject is physically safe for the duration of the seizure. This involves moving the subjects out of the rTMS chair and onto the floor lying down on his or her left side. The subject will be kept lying down on his or her left side, while the staff call emergency medical help, via a 911 call. Resources available in the laboratory include a first-aid kit and immediate phone access. A seizure constitutes a reportable adverse event, and will thus be immediately reported to the IRB via the Safety Events Form mechanism.

The most commonly reported side effect of rTMS is headache. This headache is typically of a muscle-tension type. It usually develops during or immediately after the stimulation and may last for minutes to hours following the end of the stimulation. It is typically limited to the day of stimulation, and usually responds promptly to single doses of over the counter pain medications. Neck pain or scalp pain may also occur. Both are usually managed easily with over-the-counter analgesics.

As noted in Rossi et al. (2009), Loo and colleagues reported mild and transient changes in auditory threshold in two depressed patients following a 2-4 week rTMS course of rTMS (16). Cases of tinnitus have been reported after rTMS treatments. In addition, recently in a study investigating the effects of rTMS on symptoms of depression, a patient experienced moderate to severe tinnitus after an rTMS session in which earplugs were not used. Rossi et al. recommended that hearing protection always should be worn during rTMS application, and that individuals with cochlear implants not receive rTMS. In the current study, earplugs will be worn by all subjects during rTMS procedures. Individuals with cochlear implants will be excluded from participation.

Risks to the unborn children of pregnant women receiving rTMS are unknown. Pregnant women will be excluded as per IRB policy. If sexually active, the subject must agree to use appropriate contraceptive measures for the duration of the study. Medically acceptable contraceptives include: (1) surgical sterilization (such as a tubal ligation or hysterectomy), (2) approved hormonal contraceptives (such as birth control pills, patches, implants or injections), (3) barrier methods (such as a condom or diaphragm) used with spermicide, or (4) an intrauterine device (IUD). Contraceptive measures such as Plan B (TM), sold for emergency use after unprotected sex, are not acceptable methods for routine use. If the subject has any uncertainty about whether they could be pregnant, another urine pregnancy test will be performed before they can participate in this protocol. The person(s) who will perform the urine pregnancy test will have successfully completed training as directed by the Chair of Obstetrics and Gynecology of the Duke University School of Medicine. The urine pregnancy test kits used for this research study will be those commercially available test kit specified by the Chair of Obstetrics and Gynecology and in routine use at DUHS.

Costs to the Subject – Subjects would not incur any costs because of participation in this research study. There would compensation for patients in this study. Subjects would receive standard of care and there are no additional visits as part of the study. **The study sponsor would pay for the TMS procedure.**

11. Data Analysis & Statistical Considerations

Theta Burst Stimulation in Schizophrenia

The BACS data and EEG data will be analyzed using MATLAB and done by the study coordinator. We will perform multiple t tests to see if one session of theta burst stimulation can modulate working memory performance and EEG in patients with schizophrenia. This is a pilot study and so we limit recruitment to 10 patients.

12. Data & Safety Monitoring

Data and safety monitoring will follow standard protocol procedures. Any serious adverse event will be reported within 24 hours to the Duke IRB. Adverse events will be documented and addressed accordingly. The participants will be fully informed of the nature of the study requirements prior to enrollment and periodically throughout the study. The participants' well-being will be continuously monitored by the experimenter, and the Principal Investigator will report all serious adverse events in an expedited manner to the Duke University Health System (DUHS) Institutional Review Board (IRB) office and all applicable regulatory authorities in accordance with the Center's standard operating procedures. The study monitor will be [name]. [name] will ensure the quality of the study and establish that all study staff are complying with the investigational plan and IRB regulations. Monitoring of this protocol is simplified by the fact that this study involves a small number of investigators and a single facility in which the study is being conducted. Throughout the investigation, the monitor will ensure that the facilities being used continue to be acceptable for the purposes of the study, that the investigational plan is being followed, that any changes to the protocol have received IRB approval and have been reported to the sponsor, that accurate, complete, and current records are maintained, that accurate, complete, and timely reports are made to the IRB. This will be accomplished through quarterly meetings during which the status of the protocol, investigators, and IRB compliance are reviewed. The monitor will review each research chart for completeness and accuracy. He will confirm that inclusion and exclusion criteria have been met for each subject enrolled, and compliance with all other aspects of the investigational plan are met.

13. Privacy, Data Storage & Confidentiality – see Section 12 of the e-IRB submission form and complete the questions in that section

References

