Theta Burst Stimulation for Schizophrenia

NCT03288779

Document Date: May 4, 2018

Theta Burst Stimulation in Schizophrenia

1. Protocol Title – Theta Burst Stimulation in Schizophrenia

2. Purpose of the study

Aim1: Evaluate the effect of theta burst stimulation (TBS) on working memory (WM) in patients with schizophrenia. Hypothesis 1 – There will be significant improvement in WM compared to baseline with one session of TBS.

Aim 2: Evaluate the effect of TBS on gamma and theta oscillations as measured from EEG. Hypothesis 2 – Increase in theta oscillation spectral power and decrease in spectral power of gamma oscillations with one session of TBS.

3. Background and Significance

Schizophrenia is an illness known to have cognitive deficits, with a chronic and variable course. There is extensive research on cognitive deficits, with working memory, processing speed and verbal memory being some of the domains affected(1, 2). Some modalities of treatment that have been tried to reverse these cognitive deficits are medications and cognitive behavioral therapy with minimal benefits (3). A few studies have shown modulation of working memory with routine repetitive transcranial magnetic stimulation at frequencies not exceeding 10 to 20 Hz of stimulation (4, 5). Other studies have shown the working memory to be related to gamma oscillations. A few studies have also shown that transcranial magnetic stimulation (TMS) modulates these gamma oscillations as well. There is an extensive body of literature that shows that working memory has contributions from theta and gamma oscillations in the brain. **Theta burst stimulation (TBS) is a form of transcranial magnetic stimulation (TMS)**, that entrains gamma and theta frequencies in the brain. It could be the most appropriate form of brain stimulation for improving cognition in schizophrenia patients because it has been shown to modulate brain oscillations in small samples of patients (6-9). The area for targeting would be the dorsolateral prefrontal cortex which is the site of origin of the gamma oscillations and plays a significant role in working memory (10, 11).

4. Design and Procedures

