4.3 Transcranial Magnetic Stimulation (TMS) administration

On day 2, the patient would be transported from the inpatient unit to the TMS lab in the red zone on the fifth floor following screening and consent process. They would be accompanied by nursing staff. During their visit to the TMS lab a sample TMS session including motor threshold determination will be conducted.

Treatment Sessions

On day 2, subjects would also be administered left sided theta burst stimulation (TBS) with concomitant EEG monitoring. The subject will be seated in a chair. A 64-channel electrode cap may be applied to the head for EEG recording. EMG electrodes will be applied to the right hand for motor evoked potential (MEP) recording. Subjects will perform BACS before and after the TMS session. EEG and EMG will be recorded throughout the treatment sessions. For theta burst stimulation the active motor threshold would be 80 % as used in most theta burst studies detailed in this review. Subjects would receive theta burst stimulation comprising 50 Hz bursts given at 3 to 5 Hz for close to 10 minutes which comprises 60 trains and 1800 pulses. The subject will be monitored until MEPs return to baseline. A side effects checklist will be completed at the beginning and at the end of the experimental session. All sessions will be performed by one of the protocol investigators, or by a trained and accredited research assistant supervised by the protocol investigators.

Methods:

Motor Threshold Determination:

Motor threshold (MT) is defined as the TMS pulse amplitude needed to elicit an EMG response of 50 μ V peak-to-peak average amplitude in a target muscle. MT is the standard in the field for determining the intensity of TMS for everyone to reduce seizure risk. The MEP for the right first dorsal interosseus (FDI) will be measured with EMG. The scalp region producing the largest amplitude MEP will be identified. At that scalp location, we will determine the TMS intensity eliciting average MEP amplitude of 50 μ V peak-to-peak in the first DI muscle

Theta Burst Stimulation in Schizophrenia

using an amplitude titration procedure (at least 5/10 trials). Individual MT will be used to determine the intensity of theta burst stimulation for everyone, as recommended by safety guidelines.

Application of theta burst stimulation (TBS)

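### Aim 1 working-memory contrast: on the 4.7 timetable an overnight interval of unlogged drug dosing lies between the baseline and post-TBS BACS

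*Combined protocol and SAP*

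**What the plan says.** Among the inclusion criteria, Section 5 lists "No restriction on concomitant medications given", with the hospital chart as the source. No section sets a stable-dose rule, addresses as-needed doses near testing, or says that drug, dose and time will be study data. Section 10 (Costs to the Subject) says "Subjects would receive standard of care", so ordinary ward treatment continues.

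The timing of the BACS is given in two ways:

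- The 4.7 table marks it at B (Day 1) and at Post (Day 2). The table has no medication row.
- Section 4.3, describing the Day 2 session, says "Subjects will perform BACS before and after the TMS session".

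Section 4.2 bears on this too. It introduces the study to inpatients on Day 1, seeks consent on Day 2, and places clinical assessment after consent.

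EEG appears only in 4.3: "On day 2, subjects would also be administered left sided theta burst stimulation (TBS) with concomitant EEG monitoring", and "EEG and EMG will be recorded throughout the treatment sessions".

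Hypothesis 1 (Section 2) is an improvement over baseline after one session. No sham or control arm is described. Section 11 plans a series of t tests in 10 patients and makes no use of drug data.

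**The concern.** With no control arm, each patient's own baseline is the only comparator for Aim 1. That works only if background conditions are alike at the two tests. On the 4.7 timetable, inpatients pass a night on the ward between them, with scheduled doses, possible as-needed doses and possible regimen changes. A patient who had a sedating dose before the Day 1 test and none before the Day 2 test could appear to improve. The opposite timing could hide a real gain. The t test attributes either difference to stimulation.

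At n = 10 a few such patients can move the mean. Unless timed doses are collected as study data, nobody reading the pilot result can tell whether this happened.

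**Working it through.** **Step 1: which interval applies.** Under 4.7 the Aim 1 interval is overnight. Under 4.3 it is one session, with about 10 minutes of stimulation plus set-up and monitoring. For inpatients, a Day 1 BACS would also come before the Day 2 consent described in 4.2. The three sections cannot all be followed as written. The size of the concern depends on which timing governs.

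**Step 2: which endpoint is exposed.** EEG is described only in the Day 2 session. Whatever the answer to Step 1, no overnight interval enters the EEG contrast.

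**Step 3: size for working memory.** The plan gives n = 10 (Sections 4.1 and 11) but no alpha, SD, effect size or power, so it has no figure to reproduce. Assumptions:

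- Two-sided alpha of 0.05, paired t test, no true TBS effect.
- Score SD of 1 and test-retest correlation r, so the SD of change is √(2(1−r)).
- r = 0.8, because 4.5 gives ICCs above .80, but only for the composite. The working-memory task is Digit Sequencing, for which no reliability is given, so r = 0.5 is also shown.
- k of 10 patients shifted by e score SDs. Neither k nor e is in the documents.

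The SD of change is √0.4 = 0.632 at r = 0.8 and √1.0 = 1.0 at r = 0.5. If all shifts go the same way, the bias in the mean change is k·e/10. Rejection rates are from simulation (200,000 trials):

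| k | e | Bias (score SD) | r = 0.8, one way | r = 0.5, one way | r = 0.8, random direction |
|---|---|---|---|---|---|
| 2 | 0.3 | 0.06 | 5.4% | 5.2% | 5.0% |
| 3 | 0.5 | 0.15 | 8.2% | 6.5% | 5.0% |
| 4 | 0.8 | 0.32 | 18.9% | 11.8% | 5.0% |

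For scale, significance at n = 10 needs a mean change of 2.262/√10 = 0.715 SDs of change. At r = 0.8 that is 0.715 × 0.632 = 0.45 score SD, so the middle-case bias of 0.15 is a third of it.

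**Step 4: the other direction.** A true effect of about 1.00 SD of change gives about 80% power at n = 10. At r = 0.8, one-way shifts against it cut power to about 71%, 52% and 18% in the three cases.

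**Step 5: random direction still costs precision.** Each affected patient adds e² to the variance, so the average variance of change becomes 2(1−r) + (k/10)e². In the middle case at r = 0.8 this is 0.4 + 0.3 × 0.25 = 0.475. The SD rises from 0.632 to 0.689, about 9%. In the largest case it is 0.4 + 0.4 × 0.64 = 0.656, an SD of 0.810, about 28% higher.

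**The case against.** The strongest reply is that 4.3 may govern. If so, both tests fall in one session and most of the mechanism disappears. This stands: the overnight exposure is conditional on 4.7, and the documents do not say which section prevails.

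The second reply also stands. Nothing in the documents makes the dose timing lean one way, and with random direction the false-positive rate is nominal. The one-way figures are an illustration, not a forecast.

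A third reply is that the missing control arm is the deeper weakness, since practice and time effects are also left unseparated in a self-described pilot. That is true, and a drug log does not replace a control. Dose timing is nonetheless a separate source of error that can be recorded cheaply.

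A reader might infer several stronger things that the documents do not support:

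- **That EEG is equally affected.** Only a dose shortly before or during the Day 2 session could enter that contrast.
- **That the plan permits drugs to change during the study.** The Section 5 line is an eligibility criterion. Freedom to change is inferred from the absence of a rule.
- **That enrolled patients had recently converted from involuntary status.** Section 6 says only that, should involuntary patients appear at chart screening, the team waits for conversion, which occurs once "illness symptoms have improved and are closer towards remission". It does not say that any were enrolled.
- **That the protocol treats drugs as effective on this endpoint.** Section 3 says "Some modalities of treatment that have been tried to reverse these cognitive deficits are medications and cognitive behavioral therapy", but the sentence ends by calling the benefit minimal.
- **That the information would be lost.** Inpatient charts could be searched later. What is missing is a plan to extract and use them, and outpatients screened by phone may have no such chart.
- **That the missing row in 4.7 is decisive.** The table also omits EEG and the side effects checklist. The point rests on silence throughout the document, including Section 11.

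**Conclusion.** The concern holds for working memory, conditional on the 4.7 timetable. In that case the Aim 1 contrast contains an overnight interval of unrestricted dosing that the plan neither records nor uses. The effect is added noise and, if dose timing differs systematically between the tests, bias of either sign.

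Under the assumed one-way shifts the bias is 0.06 to 0.32 score SD. The false-positive rate is about 5-19% at r = 0.8 or 5-12% at r = 0.5. The low end is negligible and the middle modest. With random direction the rate stays at 5%, at a cost in precision. The number of patients affected, the size of the shift, its direction, alpha and the Digit Sequencing reliability are all assumptions.

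The contradiction between 4.3 and 4.7 needs no assumption, and resolving it removes most of the exposure. The recommendation is worth making because it is cheap, not because the bias is shown to be large.

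**What to change.** Leave patients' treatment unchanged.

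1. Reconcile 4.2, 4.3 and 4.7 so that the Aim 1 baseline is the BACS done on Day 2 just before TBS, paired with the post-TBS BACS in the same session.
2. Add a row to 4.7 recording each psychoactive drug, dose and clock time from 24 hours before the first test to the last test. Use the medication record for inpatients and an interview for outpatients.
3. In Section 11, keep all pairs in the main analysis. Pre-specify a sensitivity analysis that excludes pairs with an as-needed psychoactive dose or regimen change either between the tests or in a stated window before the first test. The window before the first test is essential: a sedating dose before baseline would otherwise go unflagged. Exclusion should not be the main reading, because it would drop patients from a sample of 10 on events that may follow stimulation.

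The cost is one schedule row, a small record extract for about 10 patients, some rebooking of research sessions and one extra analysis line. Two limits remain. A dose taken before both tests can still wear off between them, which the log would show but not remove. A same-session retest also leaves practice effects unseparated; 4.5 mentions alternate forms for List Learning and Tower of London but not for Digit Sequencing.
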